5.4.2 Precautions for concomitant medications metabolized by CYP450 2C9

In vitro studies suggested a potential for interactions in drug metabolism between BAL27862, the active component of BAL101553, and concomitant use of drugs interfering with CYP2C9 (and to a lesser extent with CYP3A4 and CYP2C19).

Patients using concomitant medications known to interfere with CYP2C9 will not be excluded from the study. However, these patients must be carefully monitored for toxicity due to concomitant medications.

For phenytoin, due to its narrow therapeutic window, monitoring of plasma levels is recommended.

A list of known medications that are metabolized substrates, inhibitors, and inducers of CYP450 2C9 can be accessed at:

https://drug-interactions.medicine.iu.edu/MainTable.aspx.

5.4.3 Permitted use of prophylactic/supportive concomitant treatments

5.4.3.1 Anti-emetic treatment

Prophylactic anti-emetic treatment is not primarily recommended. However, once a patient has experienced \geq CTCAE grade 1 nausea or vomiting this patient may then receive prophylactic anti-emetic therapy at the discretion of the Investigator. Patients taking antiemetic treatment prior to the study may continue their treatment at the discretion of the Investigator.

5.4.3.2 Antidiarrheal treatment

The use of antidiarrheal treatment should be commenced at the first sign of abdominal cramping, loose stools or overt diarrhea. Diagnosis and appropriate management of diarrhea is mandatory.

5.4.3.3 Hematopoietic growth factors

Prophylactic treatment with granulocyte colony stimulating factor (G-CSF), or granulocyte-macrophage colony stimulating factor (GM-CSF), i.e., their use with the intention of supporting the dose density and/or intensity of BAL101553 treatment, is not recommended, and is not permitted during Cycle 1. However, patients who develop dose-limiting neutropenia (e.g., febrile neutropenia, prolonged grade 4 neutropenia) may be treated with G-CSF at the discretion of the Investigator, in accordance with applicable guidelines and the respective prescribing information. The Sponsor must be notified by the Investigator if a patient requires the use of hematopoietic growth factors.

5.4.3.4 Bisphosphonates

Bisphosphonates may be continued or initiated at the discretion of the Investigator. A dental examination and appropriate preventive dental care should be available or should be performed, and renal function should be carefully monitored.

5.4.3.5 Blood pressure elevations

Prophylactic antihypertensive treatment is not primarily recommended. If transient blood pressure elevations are observed following administration of oral BAL101553, the administration of short-acting antihypertensive drugs (such as nifedipine retard 10–20 mg or captopril 12.5–25 mg) should be considered. See Table 10 for details.

Patients may also receive chronic antihypertensive treatment (e.g., long-acting calcium channel blockers, ACE-inhibitors, angiotensin receptor blockers, thiazide diuretics or beta blockers). Additional short-acting antihypertensive medication may be given as add-on therapy (on an "as needed" basis).

Patients who experience symptomatic BP elevations (e.g., symptoms consistent with hypertensive encephalopathy, suspected intracerebral hemorrhage, stroke or transient ischemic attack, acute myocardial infarction, acute left ventricular or dissecting aortic aneurysm) should be managed and treated according to institutional standards of care.

Table 10 Blood pressure requirement for initiation and continuation of BAL101553 dosing

Systolic BP	Diastolic BP	
< 140 mmHg (Phase 1)	< 90 mmHg (Phase 1)	Required for patient eligibility at
< 160 mmHg (Phase 2a)	< 100 mmHg (Phase 2a)	screening
< 160 mmHg	< 100 mmHg	Required on study to continue long- term study treatment
< 180 mmHg	< 110 mmHg	Required to continue dosing

Recommended interventions related to blood pressure

Blood pressure	Timepoint	Recommended intervention
$SBP \ge 140 \text{ mmHg or } DBP \ge 90$ mmHg	Screening (Phase 1)	Patient ineligible unless repeat BP measurements are SBP < 140 mmHg AND DBP < 90 mmHg.
SBP ≥ 160 mmHg or DBP ≥ 100 mmHg (confirmed upon repeated measurements)	Any post-Screening study visit day	Initiate antihypertensive treatment or modify existing treatment to achieve SBP < 160 mmHg AND DBP < 100 mmHg within 6 weeks.
SBP ≥ 180 mmHg or DBP ≥ 110 mmHg (confirmed upon repeated measurements)	Any post-Screening study visit day	Withhold dose until SBP < 160 mmHg AND DBP < 100 mmHg.
Any recording of SBP > 220 mmHg or DBP > 110 mmHg	Any post-Screening study visit day	DLT: withhold dose until SBP < 160 mmHg AND DBP < 100 mmHg; then reduce dose by one level.
SBP \geq 160 mmHg or DBP \geq 100 mmHg that persists for $>$ 6 weeks despite antihypertensive treatment	Any post-Screening study visit day	DLT: withhold dose until SBP < 160 mmHg AND DBP < 100 mmHg; then reduce dose by one level.
Grade 4 hypertension	Any post-Screening study visit day	DLT: discontinue patient from study.

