3.2.2 Dose-limiting toxicity

Whenever possible, AEs will be graded according to the National Cancer Institute CTCAE v4.03 (Phase 1) or v5.0 (Phase 2a). DLT will be defined as any one of the AEs shown in Table 5 which occur during the first 28-day treatment cycle (Cycle 1) and if considered to be at least possibly related to BAL101553.

Table 5 Overview of dose-limiting toxicities

Toxicity	CTCAE criteria
Hematological	 Grade 4 Neutropenia (ANC < 0.5 × 10⁹/L) lasting for ≥ 5 consecutive days. Febrile neutropenia (ANC < 1.0 × 10⁹/L and single temperature of > 38.3 °C, or a sustained temperature of ≥ 38.0 °C for > 1 h). Grade 4 thrombocytopenia (platelet count < 25 × 10⁹/L) or grade 3 thrombocytopenia (platelet count < 50 × 10⁹/L) with bleeding. Any other ≥ grade 4 hematological AE.
Gastrointestinal	$ullet$ \geq Grade 3 nausea, vomiting or diarrhea despite appropriate pre-medication and/or management.
Hepatic	• Grade 3 AST or ALT elevations (> $5-20 \times ULN$ or baseline if baseline was abnormal) for > 7 days, or grade 4 (> $20 \times ULN$ or baseline if baseline was abnormal) for any duration.
Cardiac	 Grade 3 QTc interval prolongation (QTcF > 500 ms or > 60 ms change from baseline). Hypertension-related DLT: Any recording of SBP > 220 mmHg or DBP > 110 mmHg; or ≥ Grade 3 Hypertension (SBP ≥ 160 mmHg or DBP ≥ 100 mmHg) that cannot be controlled to Grade 2 Hypertension within 6 weeks of initiation or modification of antihypertensive treatment; or BAL101553 treatment discontinuation due to hypertension that cannot be controlled Grade 4 Hypertension Note: The need for administration of new antihypertensive medication or modification to more intensive antihypertensive medication will not be considered as DLT.
Other AEs	 AEs leading in Phase 1 to missing > 5 doses in Cycle 1, or causing a delay in the start of Cycle 2 by > 14 days. AEs which in the view of the Investigator and/or Sponsor, represent a clinically significant hazard to the patient. Any other ≥ grade 3 non-hematological AE.
Exceptions	 The following AEs will not be considered DLT unless considered to present a clinically significant hazard to the patient: Grade 3 fatigue. Grade 3 or 4 elevations in alkaline phosphatase. Grade 3 or 4 hypophosphatemia. Grade 4 lymphopenia.

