6.3.5 Vital signs

Summary statistics by disease subgroup, dose cohort and scheduled time point will be presented for each vital sign. The change from baseline will also be presented.

Summary statistics for baseline blood pressure (BP) and change from baseline (pre-dose on each study day to post-dose timepoints) will be presented by dose level for each study day. The mean maximum change from baseline (pre-dose on each study day to post-dose timepoints) will also be presented by dose levels for each study day. In case BP is collected on both arms, the average value will be taken for the analyses.

The number of patients with values outside marked reference ranges (shown below) will also be tabulated by disease subgroup, dose cohort and scheduled time point.

The vital signs marked reference ranges are:

Diastolic Blood Pressure (DBP): < 60 mmHg or > 100 mmHg.

Systolic Blood Pressure (SBP): < 80 mmHg or > 180 mmHg.

Pulse: < 40 beats/min or > 120 beats/min.

Temperature: <36.0 5 degree Celsius or >38.5 degree Celsius.

Vital sign assessments will be presented for each patient in a data listing.

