6.3.8 Prior and Concomitant medications

Medications and significant non-drug therapies prior to and after the start of the study drug will be listed by patient.

The concomitant medications taken from the start of the study drug (i.e. medications which start before and stop after first study drug administration or medications which start after first study drug administration) will be summarized by Anatomical Therapeutic Chemical (ATC) term and PT.

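### SAP 6.3.5 does not distinguish BP readings taken after antihypertensive treatment, and SAP 6.3.8 does not separate new or intensified antihypertensives or show them by dose group

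*Protocol*

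**What the plan says.** **When treatment is given.** For rises after dosing, Protocol 5.4.3.5 states: "If transient blood pressure elevations are observed following administration of oral BAL101553, the administration of short-acting antihypertensive drugs" is to be considered. Chronic treatment is also allowed. For confirmed SBP ≥ 160 or DBP ≥ 100 mmHg at any visit after screening, Table 10 recommends: "Initiate antihypertensive treatment or modify existing treatment to achieve SBP < 160 mmHg AND DBP < 100 mmHg within 6 weeks".

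**DLT status.** The note in Table 5 (Protocol 3.2.2) reads: "The need for administration of new antihypertensive medication or modification to more intensive antihypertensive medication will not be considered as DLT".

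**Planned BP summaries (SAP 6.3.5).**
- Each vital sign and its change from baseline, by disease subgroup, dose cohort and scheduled time point.
- For BP, the within-day "change from baseline (pre-dose on each study day to post-dose timepoints) will be presented by dose level for each study day".
- Also within day, the average of each patient's largest change (the mean maximum change), by dose level and study day.
- "The number of patients with values outside marked reference ranges (shown below) will also be tabulated": the limits on the high side are SBP > 180 and DBP > 100 mmHg.

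None of these has a rule for readings taken after antihypertensive treatment. Under SAP section 6, unscheduled readings are listed but not tabulated unless stated otherwise.

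**Planned medication summary (SAP 6.3.8).** One table by ATC term and preferred term covers "medications which start before and stop after first study drug administration or medications which start after first study drug administration". Protocol 8.3.2.3 asks for the summary by dose group as well. SAP 6.3.8 does not repeat this, and SAP section 7 reports no changes from the protocol's planned analysis.

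**The concern.** The treatment is triggered by the variable being summarized. Once a patient is treated, later readings reflect the study drug and the antihypertensive together, yet they enter the means in the same way as untreated readings. A pressor effect that was managed successfully can then look smaller in the time-point means and in the later-visit changes from baseline.

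The direct evidence of the effect is the number of patients who newly needed an antihypertensive or needed more of one. That number is not planned as an output. Exclusion criterion 11 admits patients already on up to two antihypertensives, so new need falls in the same table rows as background use.

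This matters because Protocol 1.4 says that vascular toxicity related to Cmax led to the 2-hour infusion being dropped, and that daily oral dosing is not associated with such toxicity. The BP tables are among the data a reader would use to judge that statement.

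**Working it through.** The plan states no figure on this point, so there is none to reproduce. The check has four steps.

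**1. Follow one patient through the planned outputs.** Take a Phase 1 patient whose SBP is confirmed between 160 and 180 mmHg, with DBP not above 100. An antihypertensive is started and BP is controlled at later visits.
- *DLT count:* not counted, under the note in Table 5.
- *Marked-range count:* not counted on SBP, because the limit of 180 lies above the treatment trigger of 160. The DBP limit of 100 is close to its trigger, so this gap concerns SBP.
- *Time-point means and later-visit change from baseline:* the treated readings enter unmarked.
- *Mean maximum within-day change:* the peak on the day of the rise is kept if it was a scheduled reading.
- *AE tables:* included if recorded as an AE. Protocol 7.1.1 makes a test result that requires therapy an AE, and Table 5 describes Grade 3 hypertension by the same 160/100 values as the trigger.
- *Medication table:* included, but not marked as new and not shown by dose group.

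The event is therefore recorded, but no output counts it as a new need by dose cohort, and the BP means do not show where it acted.

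**2. Shift in a cohort mean from treated readings.** Shift = (treated / n) × drop. Cohort sizes are from Protocol Appendix 3, Table 22. The drop of 15 to 30 mmHg is an assumption.
- n = 3: 1/3 × 15 = 5; 1/3 × 30 = 10 mmHg.
- n = 7: 1/7 × 15 = 2.1; 1/7 × 30 = 4.3 mmHg.
- n = 8: 1/8 × 15 = 1.9; 1/8 × 30 = 3.8 mmHg.
- 12% treated: 0.12 × 15 = 1.8; 0.12 × 30 = 3.6 mmHg. The 12% is the rate of drug-related hypertension in Phase 1 solid-tumor patients (Protocol Table 2). It stands in for a treatment rate, which the documents do not give.

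**3. Direction of the same-day bias.** A simulation was run on assumed inputs:
- pre-dose SBP with mean 128 and SD 11, truncated below 140;
- reading noise with SD 7;
- readings every 30 minutes to 4 h, with the effect peaking at 1.5 h;
- treatment at the first reading ≥ 160, lowering later readings by 10 or 20 mmHg.

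| True peak effect (mmHg) | Patients treated | Bias in mean change at 2.5 h (mmHg) | Bias in mean maximum change (mmHg) |
|---|---|---|---|
| 5 | 0.4–0.5% | −0.03 to −0.07 | 0 |
| 10 | 2% | −0.2 to −0.4 | 0 |
| 20 | 18% | −1.7 to −3.4 | −0.1 |
| 30 | 51% | −5.0 to −10.0 | −1.0 to −1.2 |

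Under these inputs the time-point mean is biased downward, more so as the true effect grows. The mean maximum is nearly unaffected. Treatment carried into later days was not modelled.

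**4. What Phase 1 showed.** Drug-related hypertension in solid-tumor patients (Protocol Appendix 3, Table 25) was 1/3 at 8 mg, 1/7 at 16 mg and 1/7 at 20 mg, all Grade 3–4, with none shown at 2, 4 or 30 mg. The total is 3/26 = 11.5%, which matches the stated 12%. There is no clear rise with dose.

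**The case against.** The strongest reply is that the information is not lost. Medications started after the first dose enter the ATC/preferred-term table and are listed by patient. Hypertension that needs therapy is an AE, and SAP 6.3.3 tabulates AEs by preferred term and worst grade, repeats this by cycle using the actual dose, and lists the treatment taken. Table 25 shows that this reporting works. This stands. A reader might infer from the BP and DLT rules that newly needed antihypertensives are counted nowhere; the documents do not support that.

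The mean maximum within-day change largely answers the same-day bias, which also stands. For chronic treatment, pre-dose and post-dose BP may both fall, so the effect on the within-day change is uncertain. The change from the pre-treatment baseline, which is also planned, remains exposed.

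A reader might further infer that the effect is understated most at the doses where it is largest. That is a plausible mechanism, not a finding. The documents give no treatment rates, the short-acting drugs are discretionary, and the observed hypertension counts do not rise with dose. Phase 1 is complete with its MTDs declared and Phase 2a assigns one dose level, so the dose comparison concerns the Phase 1 report. Only the visit-level point carries into Phase 2a.

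Table 5 also keeps several hypertension events as DLTs: uncontrolled Grade 3, Grade 4, readings above 220/110, and discontinuation for uncontrolled hypertension. The note covers only rises that treatment controls.

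Finally, summarizing BP as actually managed is a legitimate safety description. That argues for adding to the planned tables, not replacing them.

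**Conclusion.** The point holds as a gap in the safety analysis. SAP 6.3.5 mixes readings before and after antihypertensive treatment without marking them. Time-point means and later-visit changes from baseline can therefore understate a pressor effect, while the mean maximum within-day change is largely protected. SAP 6.3.8 pools new with ongoing drugs and omits the dose-group breakdown in Protocol 8.3.2.3.

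The size cannot be derived from the documents. The shifts of 5 to 10 mmHg in a three-patient cohort and about 2 to 4 mmHg in a cohort of seven or eight rest on one treated patient and an assumed drop of 15 to 30 mmHg. They show that small cohorts are sensitive, not that such a bias occurred. Neither the primary response analysis nor the declared MTDs are called into question. It is a low-cost improvement worth making.

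**What to change.** In SAP 6.3.5 and 6.3.8:

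1. Tabulate, by disease subgroup, dose cohort and cycle, the number of patients with an antihypertensive newly started or increased after first dose. Protocol 5.4 already has dosage, indication and start/stop dates recorded on the CRF.
2. Add a composite by the same groups: SBP ≥ 160 or DBP ≥ 100 mmHg, or a new or increased antihypertensive. State whether unscheduled and repeat readings count, since SAP section 6 otherwise leaves unscheduled readings out of tables.
3. Restore the dose-group breakdown in the SAP 6.3.8 summary.
4. Beside the planned tables, and labelled as a sensitivity summary, flag visits after a new or increased antihypertensive and repeat the visit-level BP change without them. This is preferable to carrying forward the highest reading, which imputes values selected for being high.

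The cost is SAP wording and one or two extra tables from data already collected. There are two limits. Same-day use of short-acting drugs can be identified only by date, because the protocol does not mention clock times for medications. Leaving out post-treatment visits also removes the patients who reacted most, so item 4 does not recover the untreated effect and should be read with items 1 and 2. No clinical rule needs to change.

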Blood pressure ⁶	SBP <160 and DBP <100 mmHg	SBP \geq 180 or DBP \geq 110 mmHg ⁷	Hypertension-related DLT	SBP <160 and DBP <100 mmHg	Grade 4 Hypertension
Other toxicity ⁸	\leq Grade 1 (or baseline)	\geq Grade 3	Grade 3	≤ Grade 1 (or baseline)	Grade 4

Abnormal laboratory values must be monitored at least twice per week until resolution to ≤ CTCAE grade 1, or stabilization.

¹DLT during Cycle 1, or event of equivalent severity occurring in any subsequent cycle.

² Or baseline if baseline was abnormal.

³ Consider neurology consultation if neurotoxicity occurs.

⁴Despite appropriate medication/management.

⁵ See Section 5.5.5: requires ECG monitoring, clinical assessment, blood sampling for PK assessment and increased ECG monitoring at next dosing.

⁶ SBP must be < 140 mmHg and DBP must be < 90 mmHg prior to dosing on Cycle 1 Day 1.

⁷ If not normalized on the same day.

⁸ Grade 3 fatigue; grade 3/4 alkaline phosphatase elevations, asymptomatic hypophosphatemia, or lymphopenia; do not require dose delays/modifications unless considered clinically significant.

3.2.6 **Duration of treatment**

All patients will be scheduled to receive two 28-day treatment cycles.

BAL101553 treatment may be continued after the second 28-day cycle until disease progression, occurrence of unacceptable toxicity or other criteria for withdrawal are met (see Section 4.4). To continue treatment beyond two 28-day treatment cycles, efficacy assessments scheduled at the end of at least each even-numbered cycle must be completed. Subsequent treatment cycles may not be initiated if disease progression is observed. From Cycle 6 onwards, the interval between CT/MRI scans may be extended from 8 weeks to 12 weeks.

Unless treatment is stopped due to occurrence of DLT, patients in the Phase 1 dose escalation portion of the study (Section 3.1.2) will be replaced if they could not complete at least one 28-day treatment cycle. Patients in the Phase 2 a expansion portion of the study (Simon's two-stage design, Section 3.1.3) will be replaced if they could not complete at least one post-baseline RANO assessment after having received at least 6 weeks of study treatment. Section 4.5 describes the replacement of patients who do not complete these minimum numbers of 28-day treatment cycles.

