4.3 Exclusion criteria

Patients meeting any of the following exclusion criteria at screening must not be enrolled in the study:

1. Patients with advanced or recurrent solid tumors who have received chemotherapy, radiotherapy, immunotherapy, or investigational agents within 4 weeks (2 weeks for single fraction of palliative radiotherapy, 6 weeks for nitrosoureas or mitomycin C) prior to starting study drug, or who have not recovered to ≤ Common Terminology Criteria for Adverse Events version 4.03 (CTCAE) grade ≤ 1 from all side effects of prior therapies except for residual toxicities, such as alopecia, which do not pose an ongoing medical risk.

Patients with prostate cancer must have discontinued anti-androgens (e.g., bicalutamide, nilutamide) for at least 6 weeks prior to starting study drug; chemical castration with luteinizing hormone-releasing hormone analogues can be continued.

Patients with recurrent or progressive GBM or high-grade glioma who have: received radiotherapy within 6 weeks (Phase 1) or 12 weeks (Phase 2a), unless there is a new area of enhancement consistent with recurrent tumor outside the radiation field, or there is histological confirmation of unequivocal tumor progression; received administration of prior anti-tumor chemotherapy within 4 weeks, or within 6 weeks for nitrosoureas; undergone surgical resection within 4 weeks (Phase 2a: 2 weeks) or a stereotactic biopsy/core biopsy within 1 week prior to starting study drug.

- 2. Patients who have had prior exposure to BAL101553.
- 3. Inability to swallow oral medication.
- 4. Increase in steroid dose in GBM or high-grade glioma patients within 5 days prior to first study-drug administration or requirement for > 6 mg/day dexamethasone or equivalent for symptom control.
- 5. Patients with gastrointestinal disease or those who have had a procedure that is expected to interfere with the oral absorption or tolerance of BAL101553 (e.g., functionally relevant gastrointestinal obstruction, or frequent vomiting).
- 6. Symptomatic brain metastases or leptomeningeal disease, indicative of active disease, in patients with advanced or recurrent solid tumors.
- 7. Peripheral neuropathy \geq CTCAE grade 2.
- 8. Known human immunodeficiency virus (HIV) infection.
- 9. Known acute or chronic hepatitis B or hepatitis C infection.
- 10. Systolic blood pressure (SBP) ≥ 160 mmHg or diastolic blood pressure (DBP) ≥ 100 mmHg at the screening visit.

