- 4. Complete vital signs will be obtained at Screening and at the End of Study visit. During PK sampling on D1 of Cycle 1, vital signs will be obtained pre-dose and 0.5 h, 1 h, 2 h, 3 h, 4 h, 6 h, 8 h and 24 h after intake of study medication (see Section 5.5.4). On other assessment days of Cycles 1 and 2, vital signs will be obtained prior to dosing and 0.5 h, 1 h, and 2 h after intake of the study medication. From Cycle 3 onwards complete vital signs will be obtained prior to dosing and 1 h after intake of BAL101553 study drug on D1 and D15.
- 5. On all assessment days during Cycles 1 and 2, blood pressure (BP) measurements will be obtained prior to dosing and 0.5 h, 1 h, and 2 h after intake of the study medication. From Cycle 3 onwards BP measurements will be obtained prior to dosing and 1 h after intake of the study medication. If SBP ≥ 160 mmHg or DBP ≥100 mmHg occur, BP should be monitored every 10–15 min until return to SBP/DBP < 160/90 mmHg. Patients should only be discharged home once BP levels have stabilized to SBP levels < 160 mmHg and DBP levels < 100 mmHg (see Section 5.5.4).
- 6. Single 12-lead ECGs are to be obtained as follows (see Section 5.5.5):
 - At Screening to determine study eligibility of patients and at the End of Study visit.
 - On D1 of Cycle 1: pre-dose; and 1 h, 2 h, 4 h and 8 h after intake of BAL101553 study medication (within 5 min prior to PK blood sampling; see Section 5.7.
 - On D8 and D15 of Cycle 1, and D1 and D15 of Cycle 2: pre-dose and 2 h after intake of study medication.
 - On D1 of Cycle 3 and all subsequent cycles: prior to BAL101553 administration.
 - Single 12-lead ECGs should also be obtained when patients experience SBP ≥ 180 mmHg or DBP ≥ 110 mmHg, or whenever clinical cardiovascular signs or symptoms occur.
- 7. Hematology must be performed and reviewed (see Section 5.5.7.1):
 - within 72 hours of first administration of BAL101553 on D1 of Cycle 1
 - within 24 hours prior to D1 of any subsequent Cycle
 - within 24 hours prior to administration of BAL101553 on D8, D15 and D22 of Cycle 1 and Cycle 2
 - within 24 hours prior to administration of BAL101553 on D15 of all Cycles from Cycle 3 onwards.
- 8. Biochemistry must be performed according to the same schedule as Hematology (see Section 5.5.7.2).

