5.5.4.3.2 Phase 2a Simon's two-stage design

Single BP measurements will be performed in the context of complete vital signs. In Cycles 1 and 2, BP should be obtained pre-dose and 0.5 h, 1 h, and 2 h after dosing, in Cycle 3 and all subsequent cycles BP should be obtained pre-dose and 1 h after dosing. BP measurements may be repeated if the initial pre-dose SBP is \geq 160 mmHg or DBP \geq 100 mmHg. If post-dose SBP \geq 160 mmHg or DBP \geq 100 mmHg occur, BP should be monitored every 10–15 min until return to SBP < 160 and DBP < 100 mmHg. Patients should only be discharged home once blood pressure levels have stabilized at SBP levels < 160 mmHg and DBP levels < 100 mmHg.

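### Phase 2a blood-pressure rules in Tables 5, 6 and 10 and Section 3.2.5.2 give different dosing actions for the same reading

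*Protocol*

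**What the plan says.** - **DLT rows.** Table 5 (Protocol 3.2.2) and Table 10 (Protocol 5.4.3.5) use the same trigger: "Any recording of SBP > 220 mmHg or DBP > 110 mmHg". Table 10 attaches a hold until below 160/100 mmHg, then a reduction by one level. The reduce column of Table 6 (Protocol 3.2.5.2) points to this hypertension-related DLT.
- **Hold rows.** Table 10 has a separate row for "SBP ≥ 180 mmHg or DBP ≥ 110 mmHg (confirmed upon repeated measurements"), with a hold until below 160/100 and no reduction. The upper part of Table 10 lists below 180 and below 110 as "Required to continue dosing" and mentions no confirmation. Table 6 uses the same hold thresholds, with footnote 7: "If not normalized on the same day".
- **First dose.** Table 6 footnote 6 reads "SBP must be < 140 mmHg and DBP must be < 90 mmHg prior to dosing on Cycle 1 Day 1" and names no phase. Exclusion criterion 10 (Protocol 4.3) excludes "Systolic blood pressure (SBP) ≥ 160 mmHg or diastolic blood pressure (DBP) ≥ 100 mmHg at the screening visit". Table 10 gives the matching Phase 2a screening limit, below 160/100.
- **Resuming after a DLT or DLT equivalent.** The text of 3.2.5.2 requires interruption until grade 1 or lower, or baseline. Table 10 and the Table 6 blood-pressure row give below 160/100.
- **Monitoring after dosing in Phase 2a.** Table 9 footnote 5: "BP should be monitored every 10–15 min until return to SBP/DBP < 160/90 mmHg". Section 5.5.4.3.2: "BP should be monitored every 10–15 min until return to SBP < 160 and DBP < 100 mmHg".
- **Status.** Section 3.2.5.2 calls the Table 6 criteria general guidance from which investigators may depart. Its own text on interruption after a DLT or DLT equivalent is mandatory.

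**The concern.** Two sites that follow the protocol faithfully could act differently on the same reading. The difference has lasting effects. Under 3.2.5.2, a Phase 2a DLT equivalent means interruption and, if the patient continues, a reduced dose that may not be raised again. If the same toxicity returns at the same or worse severity after a reduction, the patient must be discontinued. Whether a transient diastolic reading counts therefore decides whether a patient stays at 25 mg/day.

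It also affects what the trial reports about tolerability at that dose. SAP 6.3.1 and 6.3.3 summarise interruptions, reductions and adverse events that lead to dose modification. Those counts would partly reflect which row a site applied. Phase 2a takes single blood-pressure measurements (5.5.4.3.2), where Phase 1 took triple readings before dosing (5.5.4.3.1), so the difference between any recording and a confirmed one matters more here.

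**Working it through.** The plan states no figure on this point, so the check applies each written rule to example readings.

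**1. Readings after screening, within a cycle.** The rules are:
- Table 6 hold: (SBP ≥ 180 or DBP ≥ 110) and not normalized the same day.
- Table 10 limit to continue dosing: SBP < 180 and DBP < 110.
- Table 10 hold row: (SBP ≥ 180 or DBP ≥ 110) and confirmed.
- Tables 5 and 10, DLT: SBP > 220 or DBP > 110, any recording.

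| Reading (mmHg), settled the same day | Table 6 hold | Table 10 limit to continue | Table 10 hold row | DLT: hold and reduce |
|---|---|---|---|---|
| 150/111, confirmed | no | not met | yes | yes |
| 150/111, unconfirmed | no | not met | no | yes |
| 150/110, confirmed | no | not met | yes | no |
| 190/95, confirmed | no | not met | yes | no |
| 215/95, confirmed | no | not met | yes | no |
| 225/95, unconfirmed | no | not met | no | yes |

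The first line yields all three actions from one reading. In the second line neither hold row applies, yet the harsher DLT row does. Table 10 is also divided within itself: an unconfirmed 150/111 fails its limit to continue dosing but does not trigger its hold row.

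The band in which a reading leads to a hold without reduction, in whole mmHg, is:
- systolic: 180 to 220, that is 220 − 180 + 1 = 41 values;
- diastolic: at least 110 and not above 110, that is one value.

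**2. Cycle 1 Day 1.** Readings of 150/85 and 135/95 are within the Phase 2a screening limit (below 160/100) and fail footnote 6 (below 140/90). For Phase 2a, 5.5.4.3.2 offers a repeat pre-dose reading only from 160/100. For Phase 1, 5.5.4.3.1 offers it from 140/90, the same limit as Table 10's Phase 1 screening row. Table 10 prompts antihypertensive treatment only from a confirmed 160/100. No passage says what a Phase 2a site does with a Day 1 reading in between.

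**3. Resuming after a DLT or DLT equivalent.** Table 5 labels SBP ≥ 160 or DBP ≥ 100 as Grade 3 and treats control below that as Grade 2. A reading of 155/95 meets Table 10's condition to resume and can still be Grade 2, whereas 3.2.5.2 asks for grade 1 or lower, or baseline. The general row of Table 6 repeats the grade 1 or baseline condition and adds the specific rows to it. Read whole, Table 6 therefore agrees with 3.2.5.2. The conflict lies with Table 10, and with the Table 6 blood-pressure row if it is read alone.

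**4. Monitoring only.** At a post-dose DBP of 95 with SBP below 160, Table 9 footnote 5 continues the repeat readings and 5.5.4.3.2 stops them. Both allow discharge.

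**The case against.** The strongest reply is that the DLT provisions agree with one another. Table 5, Table 10's DLT row and Table 6's reduce column all lead to the same place, and 3.2.5.2 makes interruption mandatory. On that reading the rows are tiers: a diastolic above 110 is a DLT, and the hold rows serve lesser readings. This is a fair way to read them, and the DLT row is not itself in error. But no precedence is stated. The tiered reading also leaves the confirmation and same-day conditions with nothing to do on the diastolic side except at exactly 110 mmHg. Calling Table 6 general guidance does not settle the matter, because Table 10 is divided within itself.

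It can also be said that screening and Day 1 limits apply at different times and could both be intended. That is so. A reader might infer that every Phase 2a patient screened at 140–159 systolic or 90–99 diastolic is caught, has no route to a first dose, and so wastes tissue screening. The documents do not support this. Footnote 6 tests the Day 1 reading, chronic antihypertensive treatment is permitted (5.4.3.5), and no loss of patients is shown. What stands is that the action is not stated.

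A reader might also infer an effect on the primary endpoint. A hold or a reduction does not by itself remove a patient from the efficacy-evaluable population, and no such effect is shown. Nor does Table 9 contain a dosing rule, so its mismatch cannot lead to a hold or a DLT.

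Finally, the problem may be rare. Table 22 lists no hypertension DLT among the 26 + 28 = 54 Phase 1 patients. Table 24 shows one drug-related vascular event, grade 1–2, among 28 glioma patients. Hypertension is nonetheless a known drug effect: Table 25 shows three grade 3–4 cases among 26 solid-tumor patients (3/26 = 11.5%, given as 12% in Table 2).

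**Conclusion.** The point holds as an internal inconsistency in the Phase 2a dosing rules and should be corrected. It has three parts:
- the hold and DLT triggers for DBP above 110 or SBP above 220 mmHg;
- the phase to which the Cycle 1 Day 1 limit applies;
- the condition for resuming after a DLT or DLT equivalent.

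The Table 9 difference is separate and concerns monitoring only.

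The size cannot be put as a number of patients, because the documents give no distribution of blood-pressure readings. The Simon design's stated type I error of 3.7% and power of 81% do not depend on these rules.

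The conclusion assumes readings in whole mmHg and an event judged at least possibly drug-related, as 3.2.2 requires for a DLT. It also assumes that no document outside the protocol and SAP sets an order of precedence.

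**What to change.** In the next amendment, reconcile Tables 5, 6 and 10 with Sections 3.2.5.2 and 5.5.4.3.2 and exclusion criterion 10, so that each reading leads to one action per phase. In particular:
- State whether a single, a confirmed or a same-day-normalized reading triggers the hold row and the DLT row, and which row takes precedence where they overlap.
- State whether Table 6 footnote 6 applies to Phase 2a and, if it does, what a site does when a Day 1 reading meets the screening limit but not the footnote.
- Give one condition for resuming after a hypertension-related DLT or DLT equivalent in 3.2.5.2, Table 6 and Table 10.
- Align Table 9 footnote 5 with 5.5.4.3.2, and update the copy in SAP Table 3 footnote 5.

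The clinical team decides which limits stand; none is proposed here. The cost is table and footnote edits plus notice to sites. Sample size and analysis are unchanged.
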